2.1.2 Exclusion Criteria

- 2.1.2.1 Is currently participating and receiving study therapy or has participated in a study of an investigational agent and received study therapy or used an investigational device within 4 weeks of the first dose of treatment.
- 2.1.2.2 Has a diagnosis of immunodeficiency or is receiving systemic steroid therapy or any other form of immunosuppressive therapy within 7 days prior to the first dose of trial treatment.
- 2.1.2.3 Has a known history of active TB (Bacillus Tuberculosis)

- 2.1.2.4 Hypersensitivity to pembrolizumab or any of its excipients.
- 2.1.2.5 Has had a prior anti-cancer monoclonal antibody (mAb) within 4 weeks prior to study Day 1 or who has not recovered (i.e., \leq Grade 1 or at baseline) from adverse events due to agents administered more than 4 weeks earlier.
- 2.1.2.6 Has had prior targeted small molecule therapy, or radiation therapy within 2 weeks prior to study Day 1 or who has not recovered (i.e., \leq Grade 1 or at baseline) from adverse events due to a previously administered agent.

Note: Subjects with \leq Grade 2 neuropathy are an exception to this criterion and may qualify for the study.

Note: If subject received major surgery, they must have recovered adequately from the toxicity and/or complications from the intervention prior to starting therapy.

- 2.1.2.7 Has active autoimmune disease that has required systemic treatment in the past 2 years (i.e. with use of disease modifying agents, corticosteroids or immunosuppressive drugs). Replacement therapy (e.g., thyroxine, insulin, or physiologic corticosteroid replacement therapy for adrenal or pituitary insufficiency, etc.) is not considered a form of systemic treatment.
- 2.1.2.8 Has known active central nervous system (CNS) metastases and/or carcinomatous meningitis. Subjects with previously treated brain metastases may participate provided they are stable for 6 months (without evidence of progression by imaging for at least four weeks prior to the first dose of trial treatment and any neurologic symptoms have returned to baseline), have no evidence of new or enlarging brain metastases, and are not using steroids for at least 7 days prior to trial treatment. This exception does not include carcinomatous meningitis which is excluded regardless of clinical stability.
- 2.1.2.9 Has history of (non-infectious) pneumonitis that required steroids, evidence of interstitial lung disease or active, non-infectious pneumonitis..
- 2.1.2.10 Has an active infection requiring systemic therapy.
- 2.1.2.11 Has a history or current evidence of any condition, therapy, or laboratory abnormality that might confound the results of the trial, interfere with the subject's participation for the full duration of the trial, or is not in the best interest of the subject to participate, in the opinion of the treating investigator.
- 2.1.2.12 Has known psychiatric or substance abuse disorders that would interfere with cooperation with the requirements of the trial.
- 2.1.2.13 Is pregnant or breastfeeding, or expecting to conceive or father children within the projected duration of the trial, starting with the pre-screening or screening visit through 120 days after the last dose of trial treatment.
- 2.1.2.14 Has received prior therapy with an anti-PD-1, anti-PD-L1, or anti-PD-L2 agent.
- 2.1.2.15 Has Human Immunodeficiency Virus (HIV) (HIV 1/2 antibodies).
- 2.1.2.16 Has active Hepatitis B (e.g., HBsAg reactive) or Hepatitis C (e.g., HCV RNA [qualitative] is detected).
- 2.1.2.17 Has received a live vaccine within 30 days of planned start of study therapy

- 2.1.2.18 Concurrent use of systemic steroids, except for physiologic doses of systemic steroid replacement or local (topical, nasal, eye drops or inhaled) steroid use. Limited doses of systemic steroids (e.g., in patients with exacerbations of reactive airway disease or to prevent IV contrast allergic reaction or anaphylaxis in patients who have known contrast allergies) are allowed.
- 2.1.2.19 Serious inter-current medical illness which would interfere with the ability of the patient to carry out the treatment program.
- 2.1.2.20 Patients with second malignancy within 3 years of enrollment; Patients curatively treated non-melanoma skin cancers or carcinoma in situ of the bladder, are not excluded. Patients with MEN2 and a history of pheochromocytoma will also not be excluded. In addition patients with prostate cancer who do not require systemic therapy will not be excluded. (A secondary, minor pathologic focus of another form of thyroid cancer may be coincidentally found in 15-20% of patients with medullary thyroid cancer. In such cases, eligibility is based on the discretion of the investigator.)
- 2.1.2.21 Patients with previous history of vandetanib or cabozantinib treatment for more than 28 days of treatment (patients have discontinued treatment for 28 days before enrolling).

2.1.3 Recruitment Strategies

We have established national referral patterns from our previous study with a yeast CEA vaccine – 13-C-0095. Furthermore, many patients from the study who are still being seen at the NCI will return and enroll on this trial.

2.2 Registration Procedures

Registration will be a two-part process as patients are screened on this protocol. Authorized staff must register an eligible candidate with NCI Central Registration Office (CRO) within 24 hours of signing consent. To initially register a subject after the participant has signed the consent, complete the top portion of the registration Eligibility Checklist from the website (<http://home.ccr.cancer.gov/intra/eligibility/welcome.htm>) indicating that the patient is being registered for screening and send via encrypted email to: NCI Central Registration Office [contact]. Once eligibility is confirmed after completion of screening studies, complete the remainder of the form which is the eligibility checklist, indicating that the patient is being registered for treatment and email the completed registration checklist to the CRO at NCI Central Registration Office [contact]. After confirmation of eligibility at Central Registration Office, CRO staff will call pharmacy to advise them of the acceptance of the patient on the protocol prior to the release of any investigational agents. Verification of Registration will be forwarded electronically via e-mail to the research team. A recorder is available during non-working hours.

Subjects that do not meet screening criteria should be removed from the study following the procedure in section **3.5.3**.

2.3 Screening Evaluation

2.3.1 The following tests may be obtained any time prior to initiation of study therapy:

- Pathological confirmation of diagnosis in the Laboratory of Pathology at the NIH Clinical Center prior to starting this study when possible. Pathology reports from other hospitals and a history consistent with medullary thyroid cancer will also be sufficient for documentation of pathological confirmation.

2.3.2 The following parameters will be obtained within 8 weeks prior to initiation of study therapy:

- HIV (anti HIV 1,2 antibody)
- Hepatitis B (HBcAb IgM) and C (HCV antibody test)
- Tc-99 whole body scintigraphy (bone scan)
- CT of neck/chest/abdomen/pelvis (MRI may be substituted at investigator discretion)
- Electrocardiogram (EKG)

2.3.3 The following parameters will be obtained within 10 days prior to initiation of study therapy:

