- 2.1.1.14 Demonstrate adequate organ function as defined in [Table 2](#), all screening labs should be performed within 10 days of treatment initiation.

Table 2 Adequate Organ Function Laboratory Values

System	Laboratory Value
Hematological	
Absolute neutrophil count (ANC)	$\geq 1,000$ /mcL
Platelets	$\geq 100,000$ / mcL
Hemoglobin	≥ 9 g/dL or ≥ 5.6 mmol/L without transfusion or EPO dependency (within 7 days of assessment)
Renal	
Serum creatinine OR Measured or calculated ^a creatinine clearance (GFR can also be used in place of creatinine or CrCl)	≤ 1.5 X upper limit of normal (ULN) OR ≥ 60 mL/min for subject with creatinine levels > 1.5 X institutional ULN
Hepatic	
Serum total bilirubin	≤ 1.5 X ULN OR Direct bilirubin \leq ULN for subjects with total bilirubin levels > 1.5 ULN
AST (SGOT) and ALT (SGPT)	≤ 2.5 X ULN OR ≤ 5 X ULN for subjects with liver metastases
Albumin	≥ 2.5 mg/dL
Coagulation	
International Normalized Ratio (INR) or Prothrombin Time (PT)	≤ 1.5 X ULN unless subject is receiving anticoagulant therapy as long as PT or PTT is within therapeutic range of intended use of anticoagulants
Activated Partial Thromboplastin Time (aPTT)	≤ 1.5 X ULN unless subject is receiving anticoagulant therapy as long as PT or PTT is within therapeutic range of intended use of anticoagulants
^a Creatinine clearance should be calculated per Cockcroft-Gault equation.	

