3.3.1 Dose Modifications

Adverse events (both non-serious and serious) associated with pembrolizumab exposure may represent an immunologic etiology. These adverse events may occur shortly after the first dose or several months after the last dose of treatment. Pembrolizumab must be withheld for drug-related toxicities and severe or life-threatening AEs as per **Table 4** below. See Section 4 for supportive care guidelines, including use of corticosteroids.

Table 4. Dose Modification Guidelines for Drug-Related Adverse Events

Toxicity	Hold Treatment For Grade	Timing for Restarting Treatment	Treatment Discontinuation
Diarrhea/Colitis	2-3	Toxicity resolves to Grade 0-1	Toxicity does not resolve within 12 weeks of last dose or inability to reduce corticosteroid to 10 mg or less of prednisone or equivalent per day within 12 weeks
	4	Permanently discontinue	Permanently discontinue
AST, ALT, or Increased Bilirubin	2	Toxicity resolves to Grade 0-1	Toxicity does not resolve within 12 weeks of last dose
	3-4	Permanently discontinue (see exception below) ^a	Permanently discontinue
Type 1 diabetes mellitus (if new onset) or Hyperglycemia	T1DM or 3-4	Hold pembrolizumab for new onset Type 1 diabetes mellitus or Grade 3-4 hyperglycemia associated with evidence of beta cell failure	Resume pembrolizumab when patients are clinically and metabolically stable
Hypophysitis	2-4	Toxicity resolves to Grade 0-1. Therapy with pembrolizumab can be continued while endocrine replacement therapy is instituted	Toxicity does not resolve within 12 weeks of last dose or inability to reduce corticosteroid to 10 mg or less of prednisone or equivalent per day within 12 weeks

Toxicity	Hold Treatment For Grade	Timing for Restarting Treatment	Treatment Discontinuation
Hyperthyroidism	3	Toxicity resolves to Grade 0-1	Toxicity does not resolve within 12 weeks of last dose or inability to reduce corticosteroid to 10 mg or less of prednisone or equivalent per day within 12 weeks
	4	Permanently discontinue	Permanently discontinue
Hypothyroidism		Therapy with pembrolizumab can be continued while thyroid replacement therapy is instituted	Therapy with pembrolizumab can be continued while thyroid replacement therapy is instituted
Infusion Reaction	2 ^b	Toxicity resolves to Grade 0-1	Permanently discontinue if toxicity develops despite adequate premedication
	3-4	Permanently discontinue	Permanently discontinue

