4.1.3 Supportive Care Guidelines

Subjects should receive appropriate supportive care measures as deemed necessary by the treating investigator. Suggested supportive care measures for the management of adverse events with potential immunologic etiology are outlined below. Where appropriate, these guidelines include the use of oral or intravenous treatment with corticosteroids as well as additional anti-inflammatory agents if symptoms do not improve with administration of corticosteroids. Note that several courses of steroid tapering may be necessary as symptoms may worsen when the steroid dose is decreased. For each disorder, attempts should be made to rule out other causes such as metastatic disease or bacterial or viral infection, which might require additional supportive care. The treatment guidelines are intended to be applied when the investigator determines the events to be related to pembrolizumab.

Note: if after the evaluation the event is determined not to be related, the investigator does not need to follow the treatment guidance (as outlined below). Refer to Section **3.3.1** for dose modification.

It may be necessary to perform conditional procedures such as bronchoscopy, endoscopy, or skin photography as part of evaluation of the event.

- **Pneumonitis:**
 - For **Grade 2 events**, treat with systemic corticosteroids. When symptoms improve to Grade 1 or less, steroid taper should be started and continued over no less than 4 weeks.
 - For **Grade 3-4 events**, immediately treat with intravenous steroids. Administer additional anti-inflammatory measures, as needed.
 - Add prophylactic antibiotics for opportunistic infections in the case of prolonged steroid administration.

- **Diarrhea/Colitis:**

Subjects should be carefully monitored for signs and symptoms of enterocolitis (such as diarrhea, abdominal pain, blood or mucus in stool, with or without fever) and of bowel perforation (such as peritoneal signs and ileus).

- All subjects who experience diarrhea/colitis should be advised to drink liberal quantities of clear fluids. If sufficient oral fluid intake is not feasible, fluid and electrolytes should be substituted via IV infusion. For Grade 2 or higher diarrhea, consider GI consultation and endoscopy to confirm or rule out colitis.
- For **Grade 2 diarrhea/colitis**, administer oral corticosteroids

- For **Grade 3 or 4 diarrhea/colitis**, treat with intravenous steroids followed by high dose oral steroids.

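### Hepatitis B screening orders HBcAb IgM but not HBsAg, the marker that exclusion 2.1.2.16 names

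*Combined protocol and SAP*

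**What the plan says.** Exclusion 2.1.2.16 reads "Has active Hepatitis B (e.g., HBsAg reactive) or Hepatitis C (e.g., HCV RNA [qualitative] is detected"). It is stated as a fact about the patient and is not limited to infection already known.

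The screening tests due within 8 weeks before therapy (2.3.2) include "Hepatitis B (HBcAb IgM) and C (HCV antibody test"). No other hepatitis B assay is named there. The study calendar (3.4) has one row at screening for HIV and hepatitis B and C, without naming an assay. Appendix B lists a tube for HIV antibody but none for hepatitis.

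For HIV the two sections agree. Exclusion 2.1.2.15 says "Has Human Immunodeficiency Virus (HIV) (HIV 1/2 antibodies"), and 2.3.2 orders "HIV (anti HIV 1,2 antibody").

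Section 2.2 places the eligibility decision at the end of screening: "Once eligibility is confirmed after completion of screening studies", the rest of the eligibility checklist is completed and sent to the Central Registration Office. That office confirms eligibility before the pharmacy is told to accept the patient.

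**The concern.** An exclusion that depends on a laboratory marker works only if someone measures that marker. Here the criterion points to the surface antigen and the screening list orders an IgM antibody to the core antigen. A team that follows 2.3.2 to the letter will finish screening without the result that 2.1.2.16 gives as its example.

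What is at stake is patient safety and the reading of liver events. The protocol itself made active hepatitis B a reason not to treat. The trial enrols people with minimal symptoms who, by its own account in 10.5, would ordinarily be observed at this stage, so an avoidable risk is harder to justify. Immune-mediated hepatitis is a listed toxicity of pembrolizumab (11.1.2). If liver enzymes rise on treatment, 4.1.3 says that "attempts should be made to rule out other causes such as metastatic disease or bacterial or viral infection", and for a Grade 2 hepatic event it calls for corticosteroids. Without a baseline HBsAg, that work-up starts with no pre-treatment result for comparison. Safety is a secondary objective (1.1.2), so attribution of these events matters.

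**Working it through.** The point carries no stated figure, so there is nothing to recompute. The check is a comparison of the text.

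1. **What the exclusion names.** 2.1.2.16 names HBsAg, as an example of active hepatitis B. A patient with a reactive HBsAg meets the criterion by that example, whatever else may also count.

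2. **What screening orders.** 2.3.2 orders HBcAb IgM. The calendar row in 3.4 names no assay, so it neither orders HBsAg nor rules it out. The clinical evaluation in 2.3.3.1 is history, examination and performance status. The 10-day laboratory list in 2.3.3.2 and the pathology item in 2.3.1 contain no viral serology, so their silence adds nothing. Appendix B has no hepatitis tube. In the available text HBsAg appears only in the exclusion and HBcAb only in 2.3.2. The text removed before review falls in the background section, not in eligibility or screening.

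3. **Whether the criterion expects a test or only history.** Where the protocol relies on existing knowledge it says so: 2.1.2.3 (tuberculosis), 2.1.2.8 (CNS metastases) and 2.1.2.12 (psychiatric or substance abuse disorders) are all limited to known conditions. 2.1.2.16 has no such limit and names laboratory markers. The HIV pair shows the pattern to expect, with the same assay in criterion and screen.

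4. **Whether another step closes the gap before dosing.**
 - Registration (2.2) follows completion of the screening studies, and those do not include HBsAg.
 - History may reveal infection, and 2.1.2.11 gives the investigator discretion. Neither requires the test.
 - The AST/ALT entry limits in Table 2 admit up to 2.5 X ULN, or "≤ 5 X ULN for subjects with liver metastases". They are not a viral test.

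5. **What acts after dosing.** Liver chemistries are drawn each cycle (3.4). Table 4 holds or stops treatment for "AST, ALT, or Increased Bilirubin". These limit harm but do not keep the patient out.

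Step 2 shows the mismatch on the page. The further step, that a patient could be reactive on one assay and negative on the other, rests on general laboratory knowledge that the two tests measure different things. The documents do not describe what either assay detects or misses.

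**The case against.** The strongest reply is that the exclusion binds whatever 2.3.2 lists. The investigator must be satisfied that the patient does not have active hepatitis B, a checklist must be completed, and the Central Registration Office confirms eligibility separately. The checklist is not among the documents and may ask for an HBsAg result. This stands in part: it means that the gap may be closed in practice. It does not repair the protocol, because no available text requires the result.

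A second reply is that the criterion offers HBsAg only as an example. That is right, and it governs the remedy. A reader might infer that HBsAg should replace HBcAb IgM and decide the criterion alone. The documents do not support that: it would narrow a deliberately open exclusion, and a patient who is IgM-positive but HBsAg-negative, whom the present screen flags, would pass. The wording does not remove the mismatch, since a reactive HBsAg is excluded on any reading.

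Third, a reader might infer that every patient up to the accrual ceiling of 32 (section 8) would be cleared on the IgM test alone, or that harm is likely. Neither follows. Patients are cleared on all the criteria and the checklist, and 32 is a ceiling on enrolment, not a count at risk. The documents give no HBsAg prevalence and no carrier-specific risk on pembrolizumab. The figure in 11.1.2, 16 of 1567 patients, is for immune-mediated hepatitis, not viral hepatitis.

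Finally, a reader might extend the point to hepatitis C, where the screen is an antibody and the exclusion cites RNA. That case is weaker. A positive antibody flags the patient, who is then judged against a criterion that already names RNA. A written reflex RNA step would be a clarification only.

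**Conclusion.** Wrong as written: a minor inconsistency between eligibility and screening, with a safety consequence. The required screen orders a different hepatitis B marker from the one that the exclusion names, and no available section supplies the missing test. An HBsAg-reactive, IgM-negative patient could be registered unless the investigator adds the assay or the history reveals the infection.

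Confidence is high in the mismatch, which can be read directly from 2.1.2.16 and 2.3.2. The frequency and the harm cannot be determined from the documents, and no estimate is offered. The conclusion rests on two assumptions: that the two assays can disagree in the same patient, and that nothing outside the documents, such as the eligibility checklist, already requires HBsAg. The endpoint, the 4-of-15 rule and the sample size do not depend on this point.

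**What to change.** In 2.3.2, add HBsAg and keep HBcAb IgM. State that the HBsAg result must be available before registration for treatment under 2.2 and that a reactive result excludes the patient. Leave 2.1.2.16 otherwise as wide as it is now. Naming the assays in the calendar row (3.4) and in Appendix B would keep the sections consistent.

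The cost is a line of protocol wording and one assay on a screening draw already planned, within the existing 8-week window and without an extra visit. There may be a rare extra screen failure.

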2.3.3.1 Clinical Evaluation

- History and physical examination including vital signs (blood pressure, pulse, respiratory rate, oxygen saturation)
- ECOG performance status (see [Appendix A](#))

2.3.3.2 Laboratory studies

- Complete blood count plus differential and platelet count
- Chemistries (sodium, potassium, chloride, CO₂, creatinine, glucose, BUN, albumin, calcium, magnesium, phosphorus, alk phos, ALT, AST, total bilirubin, direct bilirubin, LD, total protein, total CK and uric acid)
- PT, PTT
- Urinalysis (may be omitted if patient is incontinent and cannot provide a urine sample)
- Serum calcitonin and CEA
- TSH
- Urine Beta-HCG for women of child-bearing age (repeated within 48 hours prior to treatment). (Serum Beta-HCG may be done if urine is positive or inconclusive).

Females of childbearing potential (FCBP): A female of childbearing potential is a sexually mature woman who:

- a) Has not undergone a hysterectomy or bilateral oophorectomy
- b) Has not been naturally postmenopausal for at least 24 consecutive months (i.e. has had menses at any time in the preceding 24 consecutive months).
- c) Has a congenital or acquired condition that prevents childbearing

In addition, patients, both male and female, should be willing to practice effective birth control during the study and for four months following the last study treatment, unless they have had a prior hysterectomy, bilateral oophorectomy, congenital conditions associated with infertility or azoospermia.

2.4 Treatment Assignment and Randomization/Stratification Procedures:

Cohorts

Number	Name	Description
1	First cohort	Patients with prior vaccine therapy
2	Second cohort	Patients without prior vaccine therapy

Arms

Number	Name	Description
1	Pembrolizumab	Pembrolizumab treatment for 2 years at Q3W

Randomization and Arm Assignment

Patients will be enrolled to Cohort 1 (previous vaccine) or Cohort 2 (no previous vaccine) based on their treatment history. This will be established at each patients' screening visit and noted on the eligibility criteria. Patients in cohort 1 and cohort 2 will be directly assigned to Arm 1.

[figure not shown]

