2 ELIGIBILITY ASSESSMENT AND ENROLLMENT

2.1 Eligibility Criteria

2.1.1 Inclusion Criteria

- 2.1.1.1 Diagnosis: Patients must have histologically confirmed medullary thyroid cancer by the Laboratory of Pathology or a pathology report and history consistent with medullary thyroid cancer. It is not uncommon for a secondary, minor pathologic focus of another form of thyroid cancer to be coincidentally found in 15-20% of patients with medullary thyroid cancer²¹. In such cases, eligibility is based on the discretion of the investigator.
- 2.1.1.2 Patients must have evidence of metastatic medullary thyroid cancer including disease that is evaluable on bone, CT scan or MRI. (Patients who are surgical candidates and potentially rendered disease free with surgical resection are not eligible.)
- 2.1.1.3 Patients must have elevated calcitonin levels greater than 40 pg/mL
- 2.1.1.4 Patients must have minimal or no disease related-symptoms (Minimal symptoms will include those that do not affect activities of daily living or pain that does not require regularly scheduled narcotics.)
- 2.1.1.5 Patients must have evaluable disease on imaging
- 2.1.1.6 No history of seizures, encephalitis, or multiple sclerosis.
- 2.1.1.7 Age \geq 18 years
- 2.1.1.8 ECOG performance status of 0-1 at study entry (Karnofsky \geq 70) (See [Appendix A](#)).
- 2.1.1.9 Female subject of childbearing potential should have a negative urine or serum pregnancy within 72 hours prior to receiving the first dose of study medication. If the urine test is positive or cannot be confirmed as negative, a serum pregnancy test will be required.
- 2.1.1.10 Female subjects of childbearing potential must be willing to use an adequate method of contraception as outlined in Section [10.6](#), Contraception, for the course of the study through 120 days after the last dose of study medication.
Note: Abstinence is acceptable if this is the usual lifestyle and preferred contraception for the subject
- 2.1.1.11 Male subjects of childbearing potential must agree to use an adequate method of contraception as outlined in Section [10.6](#), Contraception, starting with the first dose of study therapy through 120 days after the last dose of study therapy.
Note: Abstinence is acceptable if this is the usual lifestyle and preferred contraception for the subject
- 2.1.1.12 Willing to travel to the NIH for follow-up visits
- 2.1.1.13 Able to understand and sign informed consent.

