3.4 Study Calendar

Procedure	Screening/ Baseline ⁵	Treatment Cycles (21 days +/- 7 days) ¹								Cycle 9 and beyond	Post Treatment ⁶	
		C1 D1	C2 D1	C3 D1	C4 D1	C5 D1	C6 D1	C7 D1	C8 D1			
History and PE	X ²	X	X	X	X	X	X	X	X	X	X	X
Vital signs	X ²	X	X	X	X	X	X	X	X	X	X	X
Performance Score	X ²											
Height/Weight	X ³											
HIV, Hep B, C	X											
Pregnancy Test (Urine or Serum beta-HCG)	X ²											
UA ⁴	X ²											
PT/INR and PTT	X ²											
Chemistries ⁷	X ²	X	X	X	X	X	X	X	X	X	X	X
CBC	X ²	X	X	X	X	X	X	X	X	X	X	X
TSH	X ²			X	X	X	X	X	X	X	X	X
T/B/NK subsets	X ²	X	X	X	X	X	X	X	X	X	X	X
Tumor Markers: Calcitonin and CEA	X ²	X	X	X	X	X	X	X	X	X	X	X
Correlative Research Studies (research bloods see Appendix B)	X	continue at 3 month intervals									X ⁸	
Radiological Assessments (MRI or CT Neck, Ch/Abd/Pelvis, Bone Scan) ³	X	continue at 3 month intervals										
EKG ³	X	continue at 3 month intervals									X	
Biopsy (optional) ⁸												
Adverse Events		X										
Concomitant Medications		X										

¹ If patient is delayed, subsequent infusion must be at least 18 days later

Abbreviated Title: Pembrolizumab in MTC

Version Date: 3/26/18

² Must be done within 10 days prior to initiation of study therapy

³ Must be done within 8 weeks prior to initiation of study therapy, and then will be done every 3 months while patients remain on study

⁴ May be omitted if patient is incontinent and cannot provide a urine sample

⁵ Baseline/Screening requirements may also be used for Day 1 requirements if logistically necessary

⁶ Post-Therapy Assessment done 3 weeks after last treatment when logistically feasible (with a possible extension to 4 weeks if logistically necessary). Patients will be offered enrollment in the 04-C-0274 "Follow-Up Study of Subjects Previously Enrolled in Immunotherapy Studies Utilizing Gene Transfer or other Immunotherapeutic Agents" once off study.

⁷ Chemistries: sodium, potassium, chloride, CO₂, creatinine, glucose, BUN, albumin, calcium, magnesium, phosphorus, alkaline phosphatase, ALT, AST, total bilirubin, direct bilirubin, LD, total protein, total CK, uric acid

⁸ When logistically feasible, pre-treatment and post-treatment samples may be obtained from consenting patients.

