10.7 Contraception

Pembrolizumab may have adverse effects on a fetus in utero. Furthermore, it is not known if pembrolizumab has transient adverse effects on the composition of sperm.

For this trial, male subjects will be considered to be of non-reproductive potential if they have azoospermia (whether due to having had a vasectomy or due to an underlying medical condition).

Female subjects will be considered of non-reproductive potential if they are either:

- (1) postmenopausal (defined as at least 12 months with no menses without an alternative medical cause; in women < 45 years of age a high follicle stimulating hormone (FSH)

level in the postmenopausal range may be used to confirm a post-menopausal state in women not using hormonal contraception or hormonal replacement therapy. In the absence of 12 months of amenorrhea, a single FSH measurement is insufficient.);

OR

(2) have had a hysterectomy and/or bilateral oophorectomy, bilateral salpingectomy or bilateral tubal ligation/occlusion, at least 6 weeks prior to screening;

OR

(3) has a congenital or acquired condition that prevents childbearing.

Female and male subjects of reproductive potential must agree to avoid becoming pregnant or impregnating a partner, respectively, while receiving study drug and for 120 days after the last dose of study drug by complying with one of the following:

(1) practice abstinence[†] from heterosexual activity;

OR

(2) use (or have their partner use) acceptable contraception during heterosexual activity.

Acceptable methods of contraception are[‡]:

Single method (one of the following is acceptable):

- intrauterine device (IUD)
- vasectomy of a female subject's male partner
- contraceptive rod implanted into the skin

Combination method (requires use of two of the following):

- diaphragm with spermicide (cannot be used in conjunction with cervical cap/spermicide)
- cervical cap with spermicide (nulliparous women only)
- contraceptive sponge (nulliparous women only)
- male condom or female condom (cannot be used together)
- hormonal contraceptive: oral contraceptive pill (estrogen/progestin pill or progestin-only pill), contraceptive skin patch, vaginal contraceptive ring, or subcutaneous contraceptive injection

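### One item in the 2.3.3.2 definition of childbearing potential has the opposite sense to 10.7, and the pre-dose pregnancy test is 72 hours in one section, 48 hours in another and absent from the study calendar

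*Combined protocol and SAP*

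**What the plan says.** **Definition.** Section 2.3.3.2 begins "A female of childbearing potential is a sexually mature woman who" and lists three items with no stated and/or between them:

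- (a) no hysterectomy or bilateral oophorectomy;
- (b) "Has not been naturally postmenopausal for at least 24 consecutive months";
- (c) "Has a congenital or acquired condition that prevents childbearing".

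Section 10.7 works from the other side. A woman is of non-reproductive potential on any one of three grounds:

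- (1) she is "postmenopausal (defined as at least 12 months with no menses without an alternative medical cause";
- (2) she had a hysterectomy, bilateral oophorectomy, bilateral salpingectomy, or tubal ligation or occlusion at least 6 weeks before screening;
- (3) she "has a congenital or acquired condition that prevents childbearing".

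**Test timing.** Inclusion criterion 2.1.1.9 asks for a negative urine or serum test "within 72 hours prior to receiving the first dose of study medication". Section 2.3.3 places a urine beta-HCG within 10 days of starting therapy, and 2.3.3.2 adds that it is "repeated within 48 hours prior to treatment". In the study calendar (3.4) the pregnancy test row has a single mark, in the screening column. It carries the footnote "Must be done within 10 days prior to initiation of study therapy", and nothing is marked at Cycle 1 Day 1.

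**Cross-reference.** Criteria 2.1.1.10 and 2.1.1.11 send the reader to Section 10.6 for contraception. Section 10.6 is the consent process; contraception is 10.7.

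**The concern.** These are operative rules. Criteria 2.1.1.9 (test) and 2.1.1.10 (contraception) attach to women of childbearing potential, and 2.3.3.2 is the only place where that term is defined. If item (c) is applied literally together with (a) and (b), an ordinary fertile woman falls outside the label and a woman who cannot bear children falls inside it. A reader who then looks for the contraception rules is sent to the wrong section number.

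On timing, site staff commonly schedule from the calendar. If the calendar omits a test that the text requires, the test may be missed. Pregnancy is an exclusion (2.1.2.13) and Section 11.1.2 says that the drug can cause fetal harm, so both the timing of the test and who must have it bear on patient safety.

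**Working it through.** No sample size, power or event figure is involved, so there is no plan figure to reproduce. The check is of logic and of time windows.

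**Step 1: compare the two definitions over all profiles.** Take three surgical states (none; hysterectomy or bilateral oophorectomy; tubal procedure or salpingectomy), three durations of natural amenorrhoea (0, 18 and 30 months), and a condition preventing childbearing (yes or no). That gives 3 × 3 × 2 = 18 profiles.

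- 2.3.3.2, items joined by and: of childbearing potential if (a) holds, (b) holds (under 24 months) and (c) holds (condition present).
- 10.7: of reproductive potential if amenorrhoea is under 12 months, there was no listed surgery and no condition is present.

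Ten profiles agree whether (c) is taken as written or negated: all six with hysterectomy or oophorectomy, and the four others at 30 months. The remaining eight are:

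| Surgery | Amenorrhoea (months) | Condition | 2.3.3.2 as written | 2.3.3.2 with (c) negated | 10.7 |
|---|---|---|---|---|---|
| None | 0 | No | No | Yes | Yes |
| None | 0 | Yes | Yes | No | No |
| None | 18 | No | No | Yes | No |
| None | 18 | Yes | Yes | No | No |
| Tubal | 0 | No | No | Yes | No |
| Tubal | 0 | Yes | Yes | No | No |
| Tubal | 18 | No | No | Yes | No |
| Tubal | 18 | Yes | Yes | No | No |

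The last three columns answer whether the woman counts as of childbearing or reproductive potential.

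- As written, joined by and: 5 of 18 profiles disagree with 10.7. Every woman whom 2.3.3.2 includes is one whom 10.7 excludes, and the one fertile profile in 10.7 is left out of 2.3.3.2.
- As written, joined by or: 16 of 18 disagree, because nearly every woman is then included. So no choice of connective rescues the list.
- With (c) negated: 3 of 18 disagree. All three come from the menopause interval or tubal procedures, so changing (c) alone does not reconcile the sections.

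In those three residual profiles 2.3.3.2 includes the woman and 10.7 does not. On menopause and tubal procedures, then, 2.3.3.2 is the broader definition.

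**Step 2: compare the test windows.** Measured back from first dose, 10 days × 24 = 240 hours, so the limits are 48 < 72 < 240 hours. For a single negative test:

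| Age of test at first dose | 2.1.1.9 (72 h) | 2.3.3.2 repeat (48 h) | Calendar (240 h) |
|---|---|---|---|
| 24 h | Met | Met | Met |
| 60 h | Met | Not met | Met |
| 120 h | Not met | Not met | Met |

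The windows are nested. A screening test followed by a repeat in the last 48 hours meets all three. A patient handled from the calendar alone, with one test at 120 hours, meets the calendar and breaches both other sections.

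**Step 3: who is tested.** Criterion 2.1.1.9 applies to women of childbearing potential. The test line in 2.3.3.2 applies to women of child-bearing age, without using the defined term.

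**The case against.** A reader might infer that a fertile or newly pregnant woman can be dosed under the rules as written. Taken together, the documents do not support that:

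- The 2.3.3.2 test and its 48-hour repeat depend on age, not on the defined label, so item (c) does not switch them off.
- Exclusion 2.1.2.13 bars any pregnant subject, whatever the definition.
- Contraception is required by 10.7, which has its own list, and by a sentence just below item (c) that covers patients of both sexes with a few exceptions. A healthy fertile woman fits none of those exceptions. Criteria 2.1.1.10 and 2.1.1.11 name the Contraception section, so the wrong number can be worked around.
- Being fertile is not a bar to treatment. Such a woman may enroll with a negative test and contraception.
- Dosing on a 10-day-old test would breach 2.1.1.9 and 2.3.3.2, so it is not dosing within the rules.

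A reader might also divide 240 hours by 72 or 48 and treat the ratio as the size of the problem. That compares a screening test with a pre-dose test. In the text the 10-day test and the 48-hour repeat form one scheme. Nor does calendar footnote 5, which lets screening results serve for Day 1, make matters worse: the calendar lists no Day 1 pregnancy test for it to replace.

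All of this stands, and item (c) may simply have lost a negative. The differences on menopause and tubal procedures, taken by themselves, point to extra testing under 2.3.3.2, not to missed pregnancies. What the objection leaves untouched is that the sections contradict each other and that the calendar omits a required test. Exclusion 2.1.2.13 bars pregnancy but does not say when to look for it; that depends on the test whose timing is inconsistent. The birth-control sentence in 2.3.3.2 also adds a third set of exceptions, without menopause, tubal procedures or acquired conditions in women.

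**Conclusion.** The point holds as a set of contradictions in operative text. Item (c) has opposite senses in 2.3.3.2 and 10.7. The menopause interval is 24 months in one and 12 in the other. Tubal ligation and salpingectomy count in 10.7 only. The pre-dose test is within 72 hours in one section and a repeat within 48 hours in another. The calendar shows only the 10-day screening test.

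In size, 5 of 18 profiles are classified differently if the three items are joined by and, and 3 of 18 still are if (c) is negated. These are counts of logical cases, not of patients; the documents give no figure for how many women would be affected. The practical risk is conditional: if staff schedule from the calendar alone, a woman could be dosed on a test up to 240 hours old, which neither 2.1.1.9 nor 2.3.3.2 allows. The exclusion for pregnancy and the other birth-control text remain as safeguards.

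There is no statistical effect. The endpoint, the rule of 4 or more of 15 per cohort and the ceiling of 32 patients do not depend on any of this. The correction is still worth making, because the rules concern eligibility and safety and it costs little.

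**What to change.** Reconcile 2.1.1.9, 2.3.3.2, the study calendar and 10.7:

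1. Use one definition of childbearing potential throughout, with item (c) no longer contradicting 10.7, and align the exceptions in the birth-control sentence of 2.3.3.2 with it.
2. State one pre-dose test window in 2.1.1.9 and 2.3.3.2.
3. Show the pre-dose test in the calendar with its own footnote, alongside the existing screening test and its 10-day footnote.
4. Correct the references to 10.6 in 2.1.1.10 and 2.1.1.11 so that they point to the Contraception section, 10.7.

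Which menopause interval, surgical exemption and test window apply is for the sponsor to decide; this review does not choose among them.

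The cost is an amendment to protocol, calendar and eligibility checklist wording. A pre-dose test is already required by 2.1.1.9 and 2.3.3.2, so no procedure is added.
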